Topical epinephrine has been used widely in medicine and dentistry to achieve rapid hemostasis. Studies by Korkmaz et al and Gunaratane et al showed no significant hypertensive episodes and no hemodynamic parameter changes associated with placement of 1:1000 topical epinephrine. However, others have reported topical epinephrine sensitivity on only small portion of patients. These studies showed that topical epinephrine may induce significant hemodynamic changes in only a subset of patients which included the ones with preexisting cardiovascular diseases.

A literature review of prior studies investigating the effects of topical racemic epinephrine showed its effectiveness to decrease intraoperative bleeding. Degerliyurt K. et al. showed practical use of topical epinephrine without safety concerns for sinus surgery. Vickers et al. studied the cardiovascular effects of topical epinephrine pellets and 20% ferric sulfate in endodontic surgery. They found that neither agent had any statistically significant cardiovascular effects. However, subjectively, epinephrine pellets showed better hemostasis outcome than 20% ferric sulfate.

Complications associated with use of topical epinephrine are extremely rare, and changes in cardiovascular outcomes have not been shown to be statistically significant. To the best of our knowledge, no well-designed clinical trials have been conducted to assess the cardiovascular effects of topical epinephrine on gingival tissue in a pediatric population.

The overarching purpose of this split-mouth randomized pilot study was to determine the efficacy and safety of receiving treatment with topical racemic epinephrine compared to placebo, measured by cardiovascular and hemostasis outcomes. Specifically, the primary objective of this

study was to determine if the use of racemic epinephrine has any effect on heart rate, blood pressure, or cardiac rhythm in children receiving dental care under general anesthesia. We hypothesized that the use of topical racemic epinephrine would be associated with no significant change on heart rate, blood pressure, or mean arterial pressure in children receiving dental care under general anesthesia compared to patients receiving a placebo.

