## METHODS

The study was approved by the Institutional Review Board at the University of Washington (STUDY00006670). Participants and their parents/legal guardian were recruited from a pool of patients who were scheduled to receive comprehensive dental care under general anesthesia (GA) at the University of Washington Center for Pediatric Dentistry. Families were approached regarding study participation the day of the initial dental surgery consultation or were contacted by phone at least 2 days prior to their scheduled dental surgery appointment. Consent was obtained the day of the surgery. Inclusion criteria included American Academy of Anesthesiologists physical status classification (ASA) I or II, English speaking, and having caries lesions requiring prefabricated crowns on both primary maxillary first molars, teeth #B and I.

Subjects were excluded from the study if the parents or guardians were not able to communicate with the study coordinator in English or the patient had severe systemic illness (ASA III or greater), cardiac arrhythmia, cardiovascular disease, diabetes, thyroid disease and/or prescribed anti-arrhythmic, antihypertensive, or ionotropic medications. Subjects were also excluded if they required pulpotomy or pulpectomy treatment on the primary maxillary first molars.

This was a single blinded, split-mouth randomized controlled pilot study. We recruited patients from June 2019 until November 2019. Sixteen children met inclusion criteria and were approached for participation. Three patients were excluded from the study: One patient did not meet the inclusion criteria after new radiographs were taken under GA and two caregivers declined to participate in the study on the day of surgery (Figure 1).

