Randomization was performed in two stages. Using Stata 14.2 (StataCorp, College Station, TX) statistical software we first randomized whether the control treatment would be applied to the primary right or left maxillary first molar. The first randomization resulted in assignment of the right side of the mouth for the control treatment. This assignment was maintained for all participants. The second randomization step determined the treatment sequence; whether control or intervention treatment was done first. A randomization list was created and placed into a password protected Excel file prior to the start of the study. The order in which the patient received the intervention (either first or second) was randomly assigned to each patient using the randomization list.

The main objective of this method was to have each patient serve as their own control and ensure randomization of the timing (first or second) of the experimental condition. Parents were not present during the procedure, and patients were unconscious and therefore blinded to the intervention. The treating dentist and study personnel were not blinded.

Each patient's weight and medical history was updated on the day of surgery. All patients fasted for at least eight hours prior to the procedure. They were transferred to the operating room and received mask inhalation induction (8% sevoflurane and 50-70% N2O/O2). Monitoring

equipment was applied after the patient was anesthetized, and it was maintained in place throughout the course of the procedure. Vital sign measurements included capnography, oxygensaturated hemoglobin percentage (SpO2), heart rate (HR) in beats per minute (bpm), and cardiac rhythm-which was continuously recorded from a 5-lead electrocardiogram (ECG). The systolic blood pressures (SBP) and diastolic blood pressures (DBP) were measured in millimeters of mercury (mmHg) via standard automatic noninvasive arterial cuff on the ankle or upper arm.

All baseline vitals were recorded and peripheral intravenous (IV) access was obtained. Patients then received 1 to 2mg/kg of propofol, Decadron 4 to 6mg total and 0.5 mg/kg of ketorolac via IV, followed by direct laryngoscopy and nasotracheal intubation. Anesthesia was maintained throughout the procedure with a continuous IV infusion of propofol (50-100 mcg/kg/min), Remifentanil infusion (0.05-0.1 mcg/kg/min), and inhaled nitrous oxide/oxygen (30-70%).

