After successful intubation, necessary radiographs were taken, a throat pack was placed, followed by cleaning, dental examination and treatment planning. Next, the maxillary first primary molar that was randomized to be completed first was prepared to receive a zirconia crown. To reduce pressure stimulation, no dental isolation (e.g. rubber dam) was used during any of the study procedures. After preparation, an appropriately sized zirconia crown was fit, and baseline heart rate and blood pressure were recorded. Next, two saline or intervention pellets were stretched and applied directly around the gingival tissue of the prepared tooth covering the tooth circumference. Control pellets were prepared by soaking in 0.9% sodium chloride (physiological saline) whereas intervention pellets were obtained directly from the manufacturer, containing an average of 0.55 mg (0.42 to 0.68 mg/pellet) of racemic epinephrine hydrochloride per pellet (HemeRx, Racellet#3, Sprig Oral Health Technologies, Inc. Loomis, CA). Pellets were maintained in position for one

minute with gauze pressure based on manufacturer's recommendation. After pellet removal, any residual coagulum was removed using suction or moistened gauze.

Cardiovascular outcomes including patient's systolic blood pressure (SBP), diastolic blood pressure (DBP) and heart rate (HR) and mean arterial pressure (MAP) were recorded via standard automatic noninvasive arterial cuff immediately before pellet placement (baseline) and again at 1, 2, 3, 4 and 5 minutes after placement.

The adequacy of hemostasis was determined subjectively by the operating dentist/principal investigator ([name]), as "adequate" or "inadequate" at baseline and again at 1, 2, 3, 4 and 5 minutes after placement. Adequate hemostasis was defined as cessation of blood flow from gingival tissue. Inadequate hemostasis was defined as continued blow flow from gingival tissue, with blood contamination of the prepared tooth. Figures 2 and 3 demonstrate examples of adequate vs. inadequate hemostasis. Figure 4 demonstrates pre and post-op intraoral photos of maxillary arch of one of the patients.

Following study procedures, the remainder of each patient's dental care was completed, including application of rubber dam isolation, sealants, composite restorations, pulpotomies, stainless-steel crowns and extractions. All patients were discharged on the same day after adequate recovery and observation time.

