Data was analyzed using Stata SE version 14.2 (College Station, TX) software. Descriptive statistics are reported as mean and standard deviation. Paired t-test and one-way repeated analysis of variance (ANOVA) were used for comparison of cardiovascular outcomes within controls (Table 1) and within interventions (Table 2). A paired t-test with equal variance was used for comparing control and intervention cardiovascular values as well as time to hemostasis adequacy (Table 3). McNemar's Exact test was used to compare whether a patient reached adequate

hemostasis in the intervention and control sides. A p-value < 0.05 was considered to be statistically significant.

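### The cardiovascular outcomes are analysed only as group means, so with 13 children a large rise in one to three of them would usually go unseen; each child's maximum rise on both sides should be added.

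*Combined protocol and SAP*

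**What the plan says.** The statistical paragraph of METHODS gives the whole treatment of the cardiovascular outcomes:

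- Summary: "Descriptive statistics are reported as mean and standard deviation".
- Within each condition: "Paired t-test and one-way repeated analysis of variance (ANOVA) were used for comparison of cardiovascular outcomes within controls (Table 1"), and likewise within interventions (Table 2).
- Between conditions: "A paired t-test with equal variance was used for comparing control and intervention cardiovascular values as well as time to hemostasis adequacy (Table 3"). The time points that enter this comparison are not stated.

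The readings are SBP, DBP, HR and MAP, taken by automatic cuff "immediately before pellet placement (baseline) and again at 1, 2, 3, 4 and 5 minutes after placement". No maximum change per child, range, individual profile or count of children above a limit is described. Hemostasis, the secondary outcome, does have a child-level analysis: McNemar's exact test on whether each patient reached adequacy on each side.

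The INTRODUCTION reports evidence in both directions. Two cited studies "showed no significant hypertensive episodes and no hemodynamic parameter changes associated with placement of 1:1000 topical epinephrine". Others found that "topical epinephrine may induce significant hemodynamic changes in only a subset of patients which included the ones with preexisting cardiovascular diseases". The primary hypothesis is no significant change compared with placebo. METHODS excludes a child if "the patient had severe systemic illness (ASA III or greater), cardiac arrhythmia, cardiovascular disease, diabetes, thyroid disease" or certain cardiac medication applied.

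**The concern.** A test of means suits an effect that most children share. It suits poorly an effect that is large in a few children and absent in the rest: those few move the mean only slightly, and they inflate the SD that the mean is judged against. Minute-by-minute averaging dilutes the signal further if children peak at different minutes.

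The direction of the hypothesis makes this matter. Because no change is what the investigators expect, a non-significant result would be read as support for safety. Insensitivity to a small group of reactors therefore pushes the conclusion towards reassurance, in a setting where the INTRODUCTION says that no well-designed trial has examined cardiovascular effects on gingival tissue in children.

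**Working it through.** The documents give no sample-size calculation, SD, effect size or margin, so there is no planned figure to reproduce.

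**Inputs.** From METHODS: 16 children approached and 3 excluded, so n = 16 − 3 = 13 pairs, assuming that all 13 gave complete data; significance at p < 0.05, taken as two-sided because the side is not stated. Assumed, not in the documents: SD of the paired epinephrine-minus-saline difference of 5, 8 or 12 units, and an extra rise of 30 units in each reactor.

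**Step 1, noise-free illustration.** Let k of 13 children have the same difference D and the rest exactly zero. The mean is kD/13 and the variance is D²·k(13 − k)/(13·12). D cancels, leaving

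t = √(12k/(13 − k)), with 12 degrees of freedom.

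| k | t | two-sided p |
|---|---|---|
| 1 | √(12/12) = 1.00 | 0.34 |
| 2 | √(24/11) = 1.48 | 0.17 |
| 3 | √(36/10) = 1.90 | 0.08 |
| 4 | √(48/9) = 2.31 | 0.040 |

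**Step 2, with noise.** Simulated paired t-tests (40,000 trials per setting), 30-unit rise in k children, no shift in the others:

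| k | mean shift (30k/13) | significant, SD 5 | SD 8 | SD 12 |
|---|---|---|---|---|
| 1 | 2.3 | 1.5% | 3.4% | 4.6% |
| 2 | 4.6 | 4.2% | 7.8% | 8.6% |
| 3 | 6.9 | 17.3% | 18.4% | 16.4% |

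A repeat with another seed gave the same picture: about 1% to 5%, 4% to 9% and 16% to 19%. With one reactor, significance is no likelier than the 5% false-positive rate.

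**Step 3, sensitivity to a common shift.** If all 13 children also shift by 2 units, three reactors are detected in about 61% (SD 5) and 46% (SD 8) of trials. With a 3-unit shift the figures are about 81% and 61%. The low figures in Step 2 therefore belong to an effect confined to the reactors.

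**Step 4, what a count can show.** If 0 of 13 children react, the exact two-sided 95% upper limit is 1 − 0.025^(1/13) = 24.7%. One reactor gives 1/13 = 7.7% (0.2% to 36.0%), and three give 3/13 = 23.1% (5.0% to 53.8%).

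**Step 5, noise in a maximum.** Take no drug effect and independent reading noise with assumed SD 5%, 8% or 10% of baseline. The largest of five readings then exceeds a single baseline reading by more than 20% of the true baseline in about 1%, 13% and 24% of children (0.1, 1.7 and 3.1 of 13). Measured against the observed baseline reading, the range is about 2% to 27%. The 20% limit is only an example.

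**The case against.** The strongest reply is that nothing here is wrong. The objective asks whether epinephrine has any effect on heart rate, blood pressure or rhythm, in a study called a pilot, and paired mean change is a conventional answer. That stands: a child-level summary supplements the plan and does not repair it.

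Three stronger readings are tempting, and the documents do not support them.

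- A reader might infer that the background predicts a marked response in a minority of these children. It does not. The cited evidence is mixed, complications are described as extremely rare, and the only members of the sensitive subset who are named, those with cardiovascular disease, are excluded at entry. What remains is that the text says the subset included such patients and does not confine it to them.
- A reader might infer from Step 1 that up to 3 of 13 children could rise by any amount and the test would stay non-significant. That holds only if every other child differs by exactly zero. With noise, three reactors are detected in 16% to 19% of trials, and in far more if the others also shift. The arithmetic also covers one t-test, not the repeated-measures ANOVA.
- A reader might take the continuous ECG as a ready source of peak heart rate. METHODS says only "cardiac rhythm-which was continuously recorded from a 5-lead electrocardiogram (ECG"); that heart-rate values can be retrieved is not stated. Setting a continuous peak against a single baseline reading would also enlarge the bias in Step 5.

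It may also be said that a large reactor would widen the reported SD. It would, but an SD identifies neither the child nor the size of the rise, and a larger SD makes the t-test less likely to reject. Tables 1 to 3 are not in the text, so whether they show ranges cannot be checked.

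**Conclusion.** The point holds as an inexpensive improvement. As described, the analysis has no summary at the level of the child, and with 13 pairs the between-side t-test would usually miss a large rise confined to one to three children. The percentages are illustrative: they rest on the assumed SDs, a 30-unit rise, a two-sided test and no common shift. A non-significant mean change cannot by itself support absence of effect in individual children.

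Two limits apply. The 24.7% upper limit for 0 of 13 comes from the sample size, and no choice of summary removes it. Nor does the addition bring a more powerful test: exact McNemar needs at least six discordant pairs, all in one direction, for p < 0.05 (2 × 0.5⁶ = 0.031; five give 0.0625). The gain is that individual responses become visible.

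**What to change.** Keep the mean-based tests and add the following from the cuff readings already recorded:

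1. For each child and each tooth, derive the maximum rise from that tooth's pre-pellet baseline over minutes 1 to 5, for SBP, DBP, MAP and HR. Show all 13 paired values in a plot or listing.
2. Report the within-child epinephrine-minus-saline difference in maximum rise with a 95% CI.
3. A count of children above a threshold is optional, and the threshold is for the investigators to choose. If given, compare the sides as paired data (for example exact McNemar), add an exact CI, and label the count post hoc if the data have been seen. That is likely, since METHODS is in the past tense and recruitment ended in November 2019.
4. Do not set a peak heart rate from continuous ECG against a single-reading baseline.
5. Limit the safety conclusion to ASA I or II children without cardiovascular disease, and state that even 0 of 13 reactors would leave an upper limit of 24.7%.

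The cost is some analysis time and a more guarded safety statement. The downside is that a maximum of five readings is biased upward by noise, so only the paired contrast with the saline side can be interpreted; the rise on the epinephrine side alone cannot.
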